12.6. Appendix 6: Contraceptive Guidance and Collection of Pregnancy Information

Woman of Childbearing Potential (WOCBP)

A woman is considered fertile following menarche and until becoming postmenopausal unless permanently sterile (see below).

Women in the following categories are not considered WOCBP

1. Premenarchal
2. Premenopausal female with ONE of the following:
 - Documented hysterectomy
 - Documented bilateral salpingectomy
 - Documented bilateral oophorectomy

Note: Documentation can come from the study site personnel's review of participant's medical records, medical examination, or medical history interview.

3. Postmenopausal female
 - A postmenopausal state is defined as no menses for 12 months without an alternative medical cause. A high follicle-stimulating hormone (FSH) level in the postmenopausal range may be used to confirm a postmenopausal state in women not using hormonal contraception or hormonal replacement therapy (HRT). However, in the absence of 12 months of amenorrhea, a single FSH measurement is insufficient.
 - Females on HRT and whose menopausal status is in doubt will be required to use 1 of the nonhormonal highly effective contraception methods if they wish to continue their HRT during the study. Otherwise, they must discontinue HRT to allow confirmation of postmenopausal status before study enrollment.

Pregnancy Testing

- WOCBP should only be included after a confirmed menstrual period and a negative urine pregnancy test.
- Pregnancy testing will be performed at Baseline (Day 1) before study treatment administration. The urine pregnancy test at Baseline will determine study contraception and abstinence requirements as follows:
 - Pregnancy testing at Baseline (Day 1) should be performed using the urine test kit provided to the study site (FIRST RESPONSE Early Result Pregnancy Test with a high sensitivity of ≤ 6.3 mIU/mL). Participants with a negative urine pregnancy test result from this test kit may be included in the study with no pretreatment contraception or abstinence requirements.

Note: *ONLY* if the study-specific pregnancy kit provided to the study site is unavailable, a standard urine pregnancy test with a sensitivity of 25 mIU/mL may be used as an exception. A participant with a negative urine pregnancy test result from

the standard test may be included in the study *only* if the participant has used a highly effective contraception method as described in Table 10 or has practiced abstinence from penile/vaginal intercourse for at least 14 days before receiving study treatment.

- A pregnancy test will also be performed at the Test-of-Cure (Day 4 to 8) Visit.
- Pregnancy testing will be performed whenever a menstrual cycle is missed or when pregnancy is otherwise suspected.
- Urine pregnancy test kits were provided by PPD except for sites in Australia where urine pregnancy test kits were provided by Flinders and Zuellig Pharma.

Contraception Guidance – Male and Female Participants

See the section directly above regarding pregnancy testing for female participants at Baseline (Day 1) and associated pretreatment contraception and abstinence requirements. Female participants of childbearing potential who enter the study using contraception must continue to do so throughout the study.

For male and female participants, the only contraception requirement from the Baseline Visit through the TOC Visit is abstinence or the use of a male condom during intercourse. As described in Section 6.3, all participants will be instructed to abstain from sexual activity from the Baseline Visit through the TOC Visit to prevent possible re-infection with NG. If a participant refuses to abstain and is sexually active, male participants as well as male partners of female participants, of **both childbearing and nonchildbearing potential**, must use a male condom during intercourse from the Baseline Visit through completion of the TOC Visit.

Table 10 Highly Effective Contraceptive Methods

Highly Effective Contraceptive Methods That Are User Dependent^a Failure rate of <1% per year when used consistently and correctly.

Combined (estrogen- and progestogen-containing) hormonal contraception associated with inhibition of ovulation^b
 
 • oral • intravaginal • transdermal

Progestogen-only hormonal contraception associated with inhibition of ovulation^b
 
 • injectable

Highly Effective Methods That Are User Independent
 
 • implantable progestogen-only hormonal contraception associated with inhibition of ovulation^b • intrauterine device (IUD) • intrauterine hormone-releasing system (IUS) • bilateral tubal occlusion

Vasectomized partner

*(A vasectomized partner is a highly effective contraception method provided that the partner is the sole male sexual partner of the WOCBP and the absence of sperm has been confirmed. If not, an additional highly effective method of contraception should be used. **Note:** Male partners of female participants, of both childbearing and nonchildbearing potential, must use a male condom during intercourse from the Baseline Visit through completion of the TOC Visit.)*

Sexual abstinence

(Sexual abstinence is considered a highly effective method only if defined as refraining from heterosexual intercourse during the entire period of risk associated with the study treatment. The reliability of sexual abstinence needs to be evaluated in relation to the duration of the study and the preferred and usual lifestyle of the participant.)

WOCBP=woman of childbearing potential.

- a. Typical use failure rates may differ from those when used consistently and correctly. Use should be consistent with local regulations regarding the use of contraceptive methods for participants in clinical studies.
- b. Hormonal contraception may be susceptible to interaction with the study treatment, which may reduce the efficacy of the contraceptive method.

Collection of Pregnancy Information**Female participants who become pregnant**

- Investigator will collect pregnancy information on any female participant who becomes pregnant while participating in this study.
- Information will be recorded on the appropriate form and submitted to GSK/PPD within 24 hours of learning of a participant's pregnancy.
- Participant will be followed to determine the outcome of the pregnancy. The investigator will collect follow-up information on participant and neonate, which will be forwarded to GSK. Generally, follow-up will not be required for longer than 6 to 8 weeks beyond the estimated delivery date.
- Any termination of pregnancy will be reported, regardless of fetal status (presence or absence of anomalies) or indication for procedure.
- While pregnancy itself is not considered to be an adverse event (AE) or serious AE (SAE), any pregnancy complication or elective termination of a pregnancy for medical reasons will be reported as an AE or SAE.
- A spontaneous abortion is always considered to be an SAE and will be reported as such.
- Any SAE occurring as a result of a poststudy pregnancy that is considered reasonably related to the study treatment by the investigator will be reported to GSK as described in Appendix 4. While the investigator is not obligated to actively seek this information in former study participants, he or she may learn of an SAE through spontaneous reporting.

Any female participant who becomes pregnant while participating will discontinue study treatment.

12.7. Appendix 7: Genetics

USE/ANALYSIS OF DNA

- Genetic variation may impact a participant's response to therapy, susceptibility, severity and progression of disease. Variable response to therapy may be due to genetic determinants that impact drug absorption, distribution, metabolism, and excretion; mechanism of action of the drug; disease etiology; and/or molecular subtype of the disease being treated. Therefore, where local regulations and institutional review board/independent ethics committee allow, a blood sample will be collected for DNA analysis.
- DNA samples will be used for research related to gepotidacin or urogenital gonorrhea and related diseases. They may also be used to develop tests/assays (including diagnostic tests) related to gepotidacin and urogenital gonorrhea. Genetic research may consist of the analysis of 1 or more candidate genes or the analysis of genetic markers throughout the genome (or analysis of the entire genome) (as appropriate).
- DNA samples will be analyzed if it is hypothesized that this may help further understand the clinical data.
- The samples may be analyzed as part of a multi-study assessment of genetic factors involved in the response to gepotidacin or study treatments of this class. The results of genetic analyses may be reported in the clinical study report or in a separate study summary.
- The sponsor will store the DNA samples in a secure storage space with adequate measures to protect confidentiality.
- The samples will be retained while research on gepotidacin (or study treatments of this class) or urogenital gonorrhea continues but no longer than 15 years after the last participant's last visit or other period as per local requirements.

12.8. Appendix 8: Liver Safety: Required Actions and Follow-up Assessments

Phase III liver chemistry stopping and increased monitoring criteria have been designed to assure participant safety and evaluate liver event etiology.

The stopping criteria for discontinuing dosing of study treatment due to liver chemistry parameters have limited application in this study, as study treatment is only administered as 2 doses of gepotidacin over a 24-hour period starting on Day 1 or as a single intramuscular dose of ceftriaxone plus an oral dose of azithromycin on Day 1. However, if participants are found to have values consistent with the usual stopping parameters, it is appropriate to institute evaluation and monitoring criteria according to standard GSK criteria. Therefore, if defined parameters are reached, liver function tests should be evaluated as shown in the table below, which is in keeping with the liver stopping criteria, and laboratory evaluation should be instituted.

Phase III liver chemistry evaluation criteria and required follow-up assessments

Liver Chemistry Evaluation Criteria – Liver Event	
ALT Absolute	ALT \geq 8 x ULN
ALT Increase	ALT \geq 5 x ULN but <8 x ULN persists for \geq 2 weeks ALT \geq 3 x ULN but <5 x ULN persists for \geq 4 weeks
Bilirubin^{a,b}	ALT \geq 3 x ULN and bilirubin \geq 2 x ULN (>35% direct bilirubin)
INR^b	ALT \geq 3 x ULN and INR>1.5, if INR measured
Cannot Monitor	ALT \geq 5 x ULN but <8 x ULN and cannot be monitored weekly for \geq 2 weeks ALT \geq 3 x ULN but <5 x ULN and cannot be monitored weekly for \geq 4 weeks
Symptomatic^c	ALT \geq 3 x ULN associated with symptoms (new or worsening) believed to be related to liver injury or hypersensitivity
Required Actions and Follow-up Assessments	
Actions	Follow-Up Assessments

 Report the event to GSK within 24 hours Complete the liver event eCRF and complete an SAE data collection tool if the event also meets the criteria for an SAE^b Perform liver event follow-up assessments Monitor the participant until liver chemistries resolve, stabilize, or return to within baseline (see MONITORING below) 	
 Viral hepatitis serology^d Obtain INR and recheck with each liver chemistry assessment until the transaminases values show downward trend Only in those with underlying chronic hepatitis B at study entry (identified by positive hepatitis B surface antigen),

Liver Chemistry Evaluation Criteria – Liver Event	

MONITORING:
 
For bilirubin or INR criteria:
 
 Repeat liver chemistries (include ALT, AST, alkaline phosphatase, bilirubin) and perform liver event follow-up assessments within 24 hours Monitor participants twice weekly until liver chemistries resolve, stabilize, or return to within baseline A specialist or hepatology consultation is recommended 
For All other criteria:
 
 Repeat liver chemistries (include ALT, AST, alkaline phosphatase, bilirubin) and perform liver event follow-up assessments within 24 to 72 hours Monitor participants weekly until liver chemistries resolve, stabilize, or return to within baseline 	
quantitative hepatitis B DNA, and hepatitis delta antibody^e
 
 Obtain blood sample for PK analysis, within 24 hours after last dose^f Serum creatine phosphokinase and lactate dehydrogenase Fractionate bilirubin, if total bilirubin $\geq 2 \times$ ULN Obtain complete blood count with differential to assess eosinophilia Record the appearance or worsening of clinical symptoms of liver injury, or hypersensitivity, on the AE report form Record use of concomitant medications on the concomitant medications report form including acetaminophen, herbal remedies, other over-the-counter medications Record alcohol use on the liver event alcohol intake eCRF page 
For bilirubin or INR criteria:
 
 Antinuclear antibody, antismooth muscle antibody, type 1 anti-liver kidney microsomal antibodies, and quantitative total immunoglobulin G (IgG or gamma globulins). Serum acetaminophen adduct HPLC assay (quantifies potential acetaminophen contribution to liver injury in participants with definite or likely acetaminophen use in the preceding week [James, 2009]). NOTE: not required in China. Liver imaging (ultrasound, magnetic resonance, or computed tomography) and/or liver biopsy to evaluate liver disease; complete Liver Imaging and/or liver biopsy eCRFs.

AE=adverse event; ALT=alanine aminotransferase; AST=aspartate aminotransferase; eCRF=electronic case report form; HPLC=high-performance liquid chromatography; IgM=immunoglobulin M; INR=international normalized ratio; PK=pharmacokinetic; SAE=serious adverse event; ULN=upper limit of normal.

- a. Serum bilirubin fractionation should be performed if testing is available. If serum bilirubin fractionation is not immediately available, discontinue study treatment for that participant if ALT ≥ 3 x ULN **and** bilirubin ≥ 2 x ULN. Additionally, if serum bilirubin fractionation testing is unavailable, **record presence of detectable urinary bilirubin on dipstick**, indicating direct bilirubin elevations and suggesting liver injury.
- b. All events of ALT ≥ 3 x ULN **and** bilirubin ≥ 2 x ULN (>35% direct bilirubin) or ALT ≥ 3 x ULN **and** INR >1.5, if INR measured which may indicate severe liver injury (possible “Hy’s Law”), **must be reported as an SAE (excluding studies of hepatic impairment or cirrhosis)**; INR measurement is not required and the threshold value stated will not apply to participants receiving anticoagulants.
- c. New or worsening symptoms believed to be related to liver injury (such as fatigue, nausea, vomiting, right upper quadrant pain or tenderness, or jaundice) or believed to be related to hypersensitivity (such as fever, rash or eosinophilia).
- d. Includes: hepatitis A immunoglobulin M (IgM) antibody; hepatitis B surface antigen, and hepatitis B core antibody (IgM); hepatitis C RNA; cytomegalovirus IgM antibody; Epstein-Barr viral capsid antigen IgM antibody (or if unavailable, obtain heterophile antibody or monospot testing); hepatitis E IgM antibody
- e. If hepatitis delta antibody assay cannot be performed, it can be replaced with a polymerase chain reaction of hepatitis D RNA virus (where needed) [Le Gal, 2005].
- f. The PK sample may not be required for participants known to be receiving placebo or non-GSK comparator treatments. Record the date/time of the PK blood sample draw and the date/time of the last dose of study treatment prior to PK blood sample draw on the eCRF. If the date or time of the last dose is unclear, provide the participant’s best approximation. If the date/time of the last dose cannot be approximated OR a PK sample cannot be collected in the time period indicated above, do not obtain a PK sample. Instructions for sample handling and shipping are in the Study Reference Manual.

Phase III liver chemistry increased monitoring criteria

Liver Chemistry Increased Monitoring Criteria – Liver Monitoring Event	
Criteria	Actions

ALT ≥ 5 x ULN and < 8 x ULN and bilirubin < 2 x ULN without symptoms believed to be related to liver injury or hypersensitivity, and who can be monitored weekly for 2 weeks.
 
OR
 
ALT ≥ 3 x ULN and < 5 x ULN and bilirubin < 2 x ULN without symptoms believed to be related to liver injury or hypersensitivity, and who can be monitored weekly for 4 weeks.
	
 • Notify the GSK medical monitor within 24 hours of learning of the abnormality to discuss participant safety. • Participant can continue study treatment. • Participant must return weekly for repeat liver chemistries (ALT, AST, alkaline phosphatase, bilirubin) until they resolve, stabilize or return to within baseline. • If at any time participant meets the liver chemistry stopping criteria, proceed as described above. • If ALT decreases from ALT ≥ 5 x ULN and < 8 x ULN to ≥ 3 x ULN but < 5 x ULN, continue to monitor liver chemistries weekly. • If, after 4 weeks of monitoring, ALT < 3 x ULN and bilirubin < 2 x ULN, monitor participants twice monthly until liver chemistries normalize or return to within baseline.

ALT=alanine aminotransferase; AST=aspartate aminotransferase; ULN=upper limit of normal.

References

12.9. Appendix 9: Additional Guidance on Permitted and Prohibited Medications and Crediblemeds.org

For quick reference, a list of some common concomitant medications that are permitted for participants to take during the study for nausea, vomiting, pain, diarrhea, etc. per investigator discretion is provided below. A list of some of the commonly used medications that are prohibited is also provided in this appendix. Lastly, a topline overview of how to use crediblemeds.org is also provided.

A further detailed list of medications will be provided in the Study Reference Manual.

List of Concomitant Medications Permitted During the Study:

Generic Name ^a	Common Therapeutic Use(s)
Dolasetron	Nausea, vomiting
Granisetron	Nausea, vomiting
Metoclopramide	Nausea, vomiting
Palonosetron	Nausea, vomiting
Promethazine	Nausea, vomiting
Tropisetron (Only on Non-US markets)	Nausea, vomiting
Acetaminophen or paracetamol	Pain
Tramadol	Pain
Hydrocodone ER	Pain, severe
Lidocaine (solution for intramuscular injection only)	Anesthetic
Loperamide	Diarrhea
Cetirizine	Antihistamine (H ₁)
Ebastine	Antihistamine (H ₁)
Fexofenadine	Antihistamine (H ₁)
Loratadine	Antihistamine (H ₁)
Clotrimazole	Antifungal – topical, nonsystemic only
Tolnaftate	Antifungal – topical, nonsystemic only
Ketoconazole	Antifungal – topical, nonsystemic only
Tenofovir and emtricitabine	Pre-exposure prophylaxis for HIV

ER=extended release; HIV=human immunodeficiency virus; US=United States.

a. Check within each local country to assess if other generic names apply.

Note: See also Section 7.7.1 for other permitted medications.

List of Concomitant Medications Prohibited During the Study:

Generic Name^a	Common Therapeutic Use(s)
Ondansetron	Nausea, vomiting
Other investigational products	Various
Systemic antibiotics (e.g., ciprofloxacin, amoxicillin/clavulanate, cephalexin, doxycycline)	Antibiotic – all systemic
Topical and intravaginal antibiotics (e.g., clindamycin, Neomycin, polymyxin, clotrimazole, tolnaftate, ketoconazole, metronidazole)	Antibiotic – all topical and intravaginal
Systemic antifungals (e.g., itraconazole, fluconazole)	Antifungal – all systemic
Prednisolone or equivalent (refer to Section 7.7.2 for details)	Immunosuppressive therapy
Strong CYP3A4 inhibitors	See Study Reference Manual
St John's wort	Herbal, various
Succinylcholine and other nondepolarizing paralytic agents	Muscle relaxation, muscle paralysis

CYP3A4=cytochrome P450 enzyme 3A4.

a. Check within each local country to assess if other generic names apply.

Note: See also Section 7.7.2 for other prohibited medications.

Crediblemeds.org Instructions

Instructions for accessing www.crediblemeds.org and searching for an exclusionary drug due to its “Known Risk of Torsades de Pointes (TdP)” category are summarized below.

To access www.crediblemeds.org, copy and paste this link into the internet search bar:
<https://www.crediblemeds.org/>

On the main home page, there are 3 search options available. Choose the first option to search for 1 drug at a time. Free registration is required by the website.

QUICK SEARCH for drugs (Free, registration required)

- [Click Here](#) Quick Search QTdrugs List for a drug
- [Click Here](#) Scan complete QTdrugs List
- [Click Here](#) Therapeutic Options not on the QTdrugs List

Choosing that option brings you to a screen that allows for you to enter a generic or brand drug name and choose Search. If it has a Known risk of TdP (i.e., is a prohibited exclusionary medication), it will show a red triangle with an exclamation point as shown here:

Search for Drugs that Prolong QT & induce Torsades de Pointes (TdP)

Based on ongoing systematic analysis of all available evidence, CredibleMeds® places drugs into broad categories based on whether each can cause QT prolongation or TdP. These actions are highly dependent on the circumstances of each drug's use AND each patient's clinical characteristics.

Search for Drug of Interest:

Zofran (Ondansetron) - ⚠️ Drug has a Known Risk of TdP

QT/TdP Risk Categories for Drugs

[figure not shown]
- ⚠️ Known Risk of TdP** - These drugs prolong the QT interval **AND** are clearly associated with a known risk of TdP, even when taken as recommended.
- ?** Possible Risk of TdP - These drugs can cause QT prolongation **BUT** currently lack evidence for a risk of TdP when taken as recommended.
- 👤** Conditional Risk of TdP - These drugs are associated with TdP **BUT** only under certain conditions of their use (e.g. excessive dose, in patients with conditions such as hypokalemia, or when taken with interacting drugs) **OR** by creating conditions that facilitate or induce TdP (e.g. by inhibiting metabolism of a QT-prolonging drug or by causing an electrolyte disturbance that induces TdP).
- ⚠️** Drugs to Avoid in Congenital Long QT Syndrome (cLQTS) - These drugs pose a high risk of TdP for patients with cLQTS and include all those in the above three categories (KR, PR & CR) **PLUS** additional drugs that do not prolong the QT interval per se but which have a Special Risk (SR) because of their other actions.

Always check the www.crediblemeds.org website for the most up-to-date information on drugs with a Known Risk of TdP for participant safety.

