8.1.1. Liver Chemistry Evaluation Criteria

Liver chemistry stopping and increased monitoring criteria have been designed to assure participant safety and evaluate liver event etiology.

The stopping criteria for discontinuing dosing of study treatment due to liver chemistry parameters have limited application in this study, as study treatment is administered as 2 oral doses of gepotidacin over a 24-hour period starting on Day 1 or as a single dose IM dose of ceftriaxone plus an oral dose of azithromycin on Day 1. However, if participants are found to have values consistent with the usual stopping parameters, it is appropriate to institute evaluation and monitoring criteria according to standard GSK criteria. Therefore, liver function tests should be evaluated according to stopping criteria and laboratory evaluation instituted if defined parameters are reached.

Phase III liver chemistry evaluation criteria are presented in Table 4.

Table 4 Liver Chemistry Evaluation Criteria

Liver Chemistry Evaluation Criteria – Liver Event	
ALT Absolute	ALT $\geq 8 \times$ ULN
ALT Increase	ALT $\geq 5 \times$ ULN but $< 8 \times$ ULN persists for ≥ 2 weeks ALT $\geq 3 \times$ ULN but $< 5 \times$ ULN persists for ≥ 4 weeks
Bilirubin	ALT $\geq 3 \times$ ULN and bilirubin $\geq 2 \times$ ULN ($> 35\%$ direct bilirubin)
INR	ALT $\geq 3 \times$ ULN and INR > 1.5 , if INR measured
Cannot Monitor	ALT $\geq 5 \times$ ULN but $< 8 \times$ ULN and cannot be monitored weekly for ≥ 2 weeks ALT $\geq 3 \times$ ULN but $< 5 \times$ ULN and cannot be monitored weekly for ≥ 4 weeks
Symptomatic	ALT $\geq 3 \times$ ULN associated with symptoms (new or worsening) believed to be related to liver injury or hypersensitivity

ALT=alanine aminotransferase; INR=international normalized ratio; ULN=upper limit of normal.

Liver safety required actions and follow-up assessments section can be found in Appendix 8.

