9.4.4. Clinical Safety Laboratory Assessments

- Refer to Appendix 2 for the list of clinical laboratory tests to be performed and to Table 1 for the timing and frequency.
- The investigator must review the laboratory report, document this review, and record any clinically relevant changes occurring during the study in the AE section of the eCRF. The laboratory reports must be filed with the source documents. Clinically significant abnormal laboratory findings are those which are not associated with the underlying disease, unless judged by the investigator to be more severe than expected for the participant's condition.
- All laboratory tests with values considered clinically significantly abnormal during participation in the study should be repeated until the values return to normal or baseline or are no longer considered significantly abnormal by the investigator or medical monitor.
- If such values do not return to normal or baseline within a period of time judged reasonable by the investigator, the etiology should be identified and the sponsor notified.
- All protocol-required laboratory assessments, as defined in Appendix 2, must be conducted in accordance with the laboratory manual and Table 1.
- All safety laboratory tests will be performed at PPD Global Clinical Laboratory. Addresses for the central laboratories, as well as all local laboratories, are provided in the List of Clinical Laboratories Used for Human Biological Sample Analysis, which is stored in the trial master file.

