12.2. Appendix 2: Clinical Laboratory Tests

- The tests detailed in Table 9 will be performed by the central laboratory.
 - Local laboratory results are only required in the event that the central laboratory results are not available in time for response evaluation. If a local sample is required, it is important that the sample for central analysis is obtained at the same time.
- Protocol-specific requirements for inclusion or exclusion of participants are detailed in Section 6 of the protocol.
- Additional tests may be performed at any time during the study as determined necessary by the investigator or required by local regulations.

Table 9 Protocol-Required Safety Laboratory Assessments

Laboratory Assessments	Parameters			
Hematology	Platelet count	RBC Indices: MCV MCH		WBC Count With Differential: Neutrophils Lymphocytes Monocytes Eosinophils Basophils
	RBC count			
	Hemoglobin			
	Hematocrit			
Clinical Chemistry ^a	Blood urea nitrogen	Potassium	AST/SGOT	Total and direct bilirubin
	Creatinine	Sodium	ALT/SGPT	Total protein
	Glucose, nonfasting	Calcium	Alkaline phosphatase	Albumin
	Chloride	Magnesium		
Routine Urinalysis	
 • Specific gravity • pH, glucose, protein, blood, and ketones by dipstick • Microscopic examination (if blood or protein is abnormal) 			
Other Screening Tests	
 • Serum or urine alcohol and drug screen (to include at minimum: amphetamines, barbiturates, cocaine, opiates, cannabinoids, and benzodiazepines) • Urine hCG pregnancy test (as needed for women of childbearing potential)^b • Serology (HBsAg, hepatitis C virus antibody, and HIV). If serology testing was performed within 3 months prior to the first dose of study treatment and results were positive, testing at Baseline is not required. If testing was performed within 3 months and any result was negative, testing at Baseline is required. 			

ALT=alanine aminotransferase; AST=aspartate aminotransferase; eCRF=electronic case report form; HBsAg=hepatitis B surface antigen; hCG=human chorionic gonadotropin; HIV=human immunodeficiency virus; MCH=mean corpuscular hemoglobin; MCV=mean corpuscular volume; RBC=red blood cell; SGOT=serum glutamic-oxaloacetic transaminase; SGPT=serum glutamic-pyruvic transaminase; WBC=white blood cell.

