Fibrin Split Product	20 to 40 mcg/mL	41 to 50 mcg/mL	51 to 60 mcg/dL	>60 mcg/dL
Prothrombin Time (PT)	1.01 to 1.25 x ULN	1.26 to 1.5 x ULN	1.51 to 3.0 x ULN	>3 x ULN
Activated Partial Thromboplastin (APTT)	1.01 to 1.66 x ULN	1.67 to 2.33 x ULN	2.34 to 3 x ULN	>3 x ULN
Methemoglobin	5.0 to 9.9%	10.0 to 14.9%	15.0 to 19.9%	>20%

N/A=not applicable; ULN=upper limit of normal.

CHEMISTRIES				
	Grade 1	Grade 2	Grade 3	Grade 4
Hyponatremia	130 to 135 mEq/L	123 to 129 mEq/L	116 to 122 mEq/L	<116 mEq/L or abnormal sodium with mental status changes or seizures
Hypernatremia	146 to 150 mEq/L	151 to 157 mEq/L	158 to 165 mEq/L	>165 mEq/L or abnormal sodium with mental status changes or seizures
Hypokalemia	3.0 to 3.4 mEq/L	2.5 to 2.9 mEq/L	2.0 to 2.4 mEq/L or intensive replacement therapy of hospitalization required	<2.0 mEq/L or abnormal potassium with paresis, ileus, or life-threatening arrhythmia
Hyperkalemia	5.6 to 6.0 mEq/L	6.1 to 6.5 mEq/L	6.6 to 7.0 mEq/L	>7.0 mEq/L or abnormal potassium with life-threatening arrhythmia
Hypoglycemia	55 to 64 mg/dL	40 to 54 mg/dL	30 to 39 mg/dL	<30 mg/dL or abnormal glucose with mental status changes or coma
Hyperglycemia (nonfasting and no prior diabetes)	116 to 160 mg/dL	161 to 250 mg/dL	251 to 500 mg/dL	>500 mg/dL or abnormal glucose with ketoacidosis or seizures
Hypocalcemia (corrected for albumin)	8.4 to 7.8 mg/dL	7.7 to 7.0 mg/dL	6.9 to 6.1 mg/dL	<6.1 mg/dL or abnormal calcium with life-threatening arrhythmia or tetany
Hypercalcemia (corrected for albumin)	10.6 to 11.5 mg/dL	11.6 to 12.5 mg/dL	12.6 to 13.5 mg/dL	>13.5 mg/dL or abnormal calcium with life-threatening arrhythmia
Hypomagnesemia	1.4 to 1.2 mEq/L	1.1 to 0.9 mEq/L	0.8 to 0.6 mEq/L	<0.6 mEq/L or abnormal magnesium with life-threatening arrhythmia
Hypophosphatemia	2.0 to 2.4 mg/dL	1.5 to 1.9 mg/dL or replacement Rx required	1.0 to 1.4 mg/dL intensive therapy or hospitalization required	<1.0 mg/dL or abnormal phosphate with life-threatening arrhythmia
Hyperbilirubinemia (when accompanied by any increase in other liver function test)	1.1 to <1.25 x ULN	1.25 to <1.5 x ULN	1.5 to 1.75 x ULN	>1.75 x ULN
Hyperbilirubinemia (when other liver function tests are in the normal range)	1.1 to <1.5 x ULN	1.5 to <2.0 x ULN	2.0 to 3.0 x ULN	>3.0 x ULN
Blood urea nitrogen	1.25 to 2.5 x ULN	2.6 to 5 x ULN	5.1 to 10 x ULN	>10 x ULN

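### Appendix 8 liver rules leave a gap: raised ALT with bilirubin ≥2×ULN that is mainly indirect meets neither table at first detection

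*Protocol*

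**What the plan says.** Protocol Section 8.1.1 (Table 4) and Appendix 8 define a liver event by the same set of rows:

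- **ALT Absolute:** ALT ≥8×ULN.
- **ALT Increase:** ALT 5 to <8×ULN persisting at least 2 weeks, or 3 to <5×ULN persisting at least 4 weeks.
- **Bilirubin:** ALT ≥3×ULN with bilirubin at least 2 "x ULN (>35% direct bilirubin").
- **INR:** ALT ≥3×ULN with INR >1.5, if INR was measured. A footnote says that measuring it is not required.
- **Cannot Monitor:** ALT in either of the lower bands when weekly monitoring is not possible.
- **Symptomatic:** ALT ≥3×ULN with symptoms attributed to liver injury or hypersensitivity.

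The increased-monitoring table in Appendix 8 has two ALT bands, 5 to <8×ULN and 3 to <5×ULN. Each requires bilirubin below 2×ULN, no symptoms and feasible weekly monitoring. The lower band reads "ALT ≥ 3 x ULN and < 5 x ULN and bilirubin < 2 x ULN without symptoms". Neither band mentions the direct fraction. The actions include "Notify the GSK medical monitor within 24 hours of learning of the abnormality to discuss participant safety", and a mandatory weekly return for liver chemistries until they resolve, stabilize or return to baseline.

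Outside Appendix 8, Section 9.4.4 says that "values considered clinically significantly abnormal during participation in the study should be repeated". If values do not normalise in a time the investigator judges reasonable, "the etiology should be identified and the sponsor notified". Appendix 2 (Table 9) lists "Total and direct bilirubin" in the central chemistry panel.

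**The concern.** One table's bilirubin condition carries a direct-fraction qualifier and the other's does not, so bilirubin ≥2×ULN with direct fraction ≤35% can fall between them. Read literally, the rule then asks for less follow-up at a higher bilirubin. With ALT 4×ULN and bilirubin 1.9×ULN, Appendix 8 requires notification within 24 hours and weekly chemistries. With the same ALT and bilirubin 2.0×ULN (direct 30%), it requires neither.

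The protocol's own grading treats the second pattern as serious. In the Appendix 5 chemistry table, the row "Hyperbilirubinemia (when accompanied by any increase in other liver function test") puts anything above 1.75×ULN at Grade 4, with no direct-fraction condition. Both ingredients can also enter the trial. Section 6.2 allows Gilbert's syndrome, isolated raised bilirubin with a direct fraction below 35%, and asymptomatic viral hepatitis.

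What is at stake is timely follow-up of individual participants, not any efficacy conclusion.

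**Working it through.** The plan states no figure to reproduce. The check is one of logical coverage.

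**Row by row at first detection.** Take ALT 4×ULN, bilirubin 2.0×ULN, direct 30%, no symptoms, INR not measured, weekly monitoring possible.

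| Rule | Met? | Reason |
|---|---|---|
| ALT Absolute | No | 4 < 8 |
| ALT Increase | No | persistence not yet shown |
| Bilirubin | No | direct 30% is not >35% |
| INR | No | not measured |
| Cannot Monitor | No | can be monitored |
| Symptomatic | No | no symptoms |
| Increased monitoring | No | bilirubin is not <2×ULN |

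**Enumeration.** Both tables were coded as yes/no rules over ALT {3, 4, 5, 6, 7.9, 8, 10}×ULN, bilirubin {0.8, 1.9, 2.0, 2.5, 4}×ULN, direct fraction {10, 35, 36, 60}%, INR {unmeasured, 1.2, 1.6}, symptoms yes/no and weekly monitoring yes/no.

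- Profiles at first detection: 7 × 5 × 4 × 3 × 2 × 2 = 1,680.
- Meeting neither table: 5 ALT values below 8 × 3 bilirubin values ≥2 × 2 direct fractions ≤35% × 2 INR levels ≤1.5 or unmeasured = 60, all asymptomatic and monitorable. Nothing else in the grid is uncovered.
- Asymptomatic profiles in that ALT, bilirubin and direct-fraction region: 5 × 3 × 2 × 3 INR levels × 2 monitoring levels = 180. So 60 of 180 are uncovered.
- With ALT persistence shown: 0 of 1,680 uncovered, because the ALT Increase row applies.

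A second grid of 1,536 profiles with different cut-points isolates the same cell: 4 × 2 × 2 × 3 = 48 uncovered, none outside it. These are counts of logical combinations, not patient frequencies.

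**How many participants.** The documents give no rates. Assume 1% to 4% have mainly indirect bilirubin ≥2×ULN, 0.5% to 2% have ALT ≥3×ULN at test of cure, and the two are independent:

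- low: 620 × 0.01 × 0.005 = 0.03
- high: 620 × 0.04 × 0.02 = 0.50

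This is before removing participants with symptoms, INR >1.5 or no possibility of weekly monitoring.

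**Effect of the proposed clause.** Uncovered profiles fall from 60 to 0 in the first grid and from 48 to 0 in the second. Profiles meeting both tables at first detection rise from 40 (5 ALT × 2 bilirubin × 4 direct, all with INR 1.6) to 70 (adding 5 × 3 × 2 = 30, again all with INR 1.6). The monitoring table already sends anyone who meets the stopping criteria to the event table, so the overlap causes no conflict.

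**The case against.** The case against giving this weight runs as follows.

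- **Other provisions apply.** Section 9.4.4 requires the investigator to review every laboratory report. Appendix 4 obliges the investigator to arrange further measurements for adverse events. Section 9 asks for immediate safety concerns to be raised with the sponsor, for gepotidacin participants deciding on further dosing. An internal team reviews blinded safety data. An investigator would hardly dismiss Grade 3 ALT with Grade 4 bilirubin. This stands: the participant is unlikely to be ignored. But none of these provisions sets a 24-hour limit or a weekly schedule.
- **Cannot Monitor may catch it.** Chemistry is scheduled only at baseline and test of cure, so weekly monitoring needs extra visits; if they cannot be arranged, that row applies. True, but the gap concerns participants who can be monitored. The ALT Increase row closes it later only if repeat tests are done, and Appendix 8 does not require them here.
- **Footnote a of Appendix 8.** It acts only when fractionation is not immediately available, and then by stopping treatment and recording a urine dipstick result. Direct bilirubin is in the central panel, so this is not the usual case.
- **Dosing is over within about a day, and the >35% condition looks deliberate.** Both are fair. They support leaving the event table alone; they do not explain less follow-up at a higher bilirubin.
- **The grid omits two situations:** an unavailable direct fraction, and the footnote exempting participants on anticoagulants from the INR threshold. This limits the statement that no other profile is uncovered to the grids used. It does not affect the cell described.
- **The step-down to twice-monthly testing requires bilirubin <2×ULN,** which a participant with stable indirect hyperbilirubinaemia would not reach. Correct, but weekly testing can still end when values stabilise.

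**Conclusion.** The gap is real. At first detection it consists of ALT 3 to <8×ULN, bilirubin ≥2×ULN, direct fraction ≤35%, INR unmeasured or ≤1.5, no symptoms and feasible weekly monitoring. Each qualifier is needed, and within the grids examined no other profile is uncovered.

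The severity is minor. The expected count is below one participant under the assumed rates and independence; a positive association between the two abnormalities would raise it, and the documents allow no check. Judgement-based follow-up under Section 9.4.4 makes repeat testing likely, though neither timed nor mandatory. SAP Section 8.3 tabulates ALT or AST >3×ULN with total bilirubin >2×ULN without a direct-fraction condition, so nearly all such cases would be reported. Confidence in the reading of the two tables is high.

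**What to change.** In both bands of the Appendix 8 increased-monitoring criteria, replace the bilirubin condition with: *bilirubin < 2 x ULN, or ≥ 2 x ULN with direct bilirubin ≤ 35%*. Leave Table 4, the liver-event table and the serious adverse event reporting rule unchanged. No SAP change is needed.

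The cost is one clause in two places, using measurements already taken, and a few extra repeat chemistries in very few participants. The existing rule that weekly testing ends when values resolve, stabilise or return to baseline prevents indefinite visits for stable indirect hyperbilirubinaemia. The twice-monthly step-down could be aligned in the same edit as an optional tidy-up.
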